#### **10.1.2 Additional Analyses of the Primary Endpoint**

Separate analyses in the combined population will be performed in subjects treated with enzalutamide + radium-223 and subjects treated with enzalutamide alone. If a bone marker test is missed at a given time point, every effort will be made to obtain the bone marker levels as early as possible. If two subsequent bone marker tests are missed, patient will excluded from the analysis.

Based on the data from the SWOG 0421 study, the estimated baseline mean and standard deviation of log2 N-telopeptides are 3.95 nM and 1.14 nM respectively. We further assume the Pearson correlation of baseline and follow up N-telopeptides is 0.50. With 35 evaluable subjects there will be 80% power to detect a change of 0.556 in log2 N-telopeptides using a paired t-test. Extrapolating from SWOG0421, a decrease of 0.556 in log2 N-telopeptide concentration would translate into an approximate 20% increase in median overall survival.

#### **10.1.3 Primary Safety Analyses**

An overall proportion of subjects with grade 3 or higher hematologic adverse events significantly higher than those reported for the radium-223 arm of

Parker et al. (2013) would be evidence of unacceptable toxicity. The sum of the proportion of subjects in Parker et al. (2013) with grade 3+ anemia, thrombocytopenia, or neutropenia is 21%. An exact binomial test will be performed at the one sided 0.05 significance level comparing the proportion of subjects with one or more of grade 3+ anemia, thrombocytopenia, or neutropenia to 21%. With a safety population of 35 evaluable patients, 13 or more patients with one or more of grade 3+ anemia, grade 3+ thrombocytopenia, or grade 3+ neutropenia would indicate an unacceptable hematologic adverse event rate.

Exact 90% confidence intervals will be calculated for adverse events and serious AEs. With 35 evaluable patients an exact 90% confidence interval for an AE will extend no more than 17.5% from the observed proportion, and there is a 90% probability that an adverse event with a probability of 6.4% will be observed at least once.

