	
hypothesis is rejected at the 0.1 significance level an additional ANCOVA model allowing for unequal variances will be fit.
 
Additional Analyses of the Primary Endpoint
 
Separate analysis in the combined population will be performed in subjects treated with enzalutamide + radium-223 and subjects treated with enzalutamide alone. If a bone marker test is missed at a given time point, every effort will be made to obtain the bone marker levels as early as possible. If two subsequent bone marker tests are missed, patient will excluded from the analysis. Based on the data from the SWOG 0421 study, the estimated baseline mean and standard deviation of log2 N-telopeptides are 3.95 nM and 1.14 nM respectively. We further assume the Pearson correlation of baseline and follow up N-telopeptides is 0.50. With 35 evaluable subjects there will be 80% power to detect a change of 0.556 in log2 N-telopeptides using a paired t-test. Extrapolating from SWOG0421, a decrease of 0.556 in log2 N-telopeptide concentration would translate into an approximate 20% increase in median overall survival.
 
Primary Safety Analyses
 
An overall proportion of subjects with grade 3 or higher hematologic adverse events significantly higher than those reported for the radium-223 arm of Parker et al. (2013) would be evidence of unacceptable toxicity. In that study the sum of the proportion of subjects with grade 3+ anemia, thrombocytopenia, or neutropenia is 21%. An exact binomial test will be performed at the one sided 0.05 significance level comparing the proportion of subjects with one or more of grade 3+ anemia, thrombocytopenia, or neutropenia to 21%. With a safety population of 35 evaluable patients, 13 or more patients with one or more of grade 3+ anemia, thrombocytopenia, or neutropenia would indicate an unacceptable hematologic adverse event rate.
 
Exact 90% confidence intervals will be calculated for adverse events (AEs) and serious AEs (SAEs). With 35 evaluable patients an exact 90% confidence interval for an AE will extend no more than 17.5% from the observed proportion, and there is a 90% probability that an adverse event with a probability of 6.4% will be observed at least once.
 
Secondary Endpoint Analyses
 
All other statistical analyses will be descriptive in nature. Please refer to section 10.2 for additional detail.

--	--

[figure not shown]

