### ***Bone Marrow Suppression***

In the randomized trial, 2% of patients on the Radium Ra 223 dichloride arm experienced bone marrow failure or ongoing pancytopenia compared to no patients treated with placebo. There were two deaths due to bone marrow failure and for 7 of 13 patients treated with Radium Ra 223 dichloride, bone marrow failure was ongoing at the time of death. Among the 13 patients who experienced bone marrow failure, 54% required blood transfusions. Four percent (4%) of patients on the Radium Ra 223 dichloride arm and 2% on the placebo arm permanently discontinued therapy due to bone marrow suppression.

In the randomized trial, deaths related to vascular hemorrhage in association with myelosuppression were observed in 1% of Radium Ra 223 dichloride-treated patients compared to 0.3% of patients treated with placebo. The incidence of infection-related deaths (2%), serious infections (10%), and febrile neutropenia (< 1%) were similar for patients treated with Radium Ra 223 dichloride and placebo.

Myelosuppression; notably thrombocytopenia, neutropenia, pancytopenia, and leukopenia; has been reported in patients treated with Radium Ra 223 dichloride. In the randomized trial, complete blood counts (CBCs) were obtained every 4 weeks prior to each dose and the nadir CBCs and times of recovery were not well characterized. In a separate single-dose phase 1 study of Radium Ra 223 dichloride, neutrophil and platelet count nadirs occurred 2 to 3 weeks after Radium Ra 223 dichloride administration at doses that were

up to 1 to 5 times the recommended dose, and most patients recovered approximately 6 to 8 weeks after administration.

In the radium-223 arm of the Phase 3 clinical trial reported in Parker et al. (2013), 12.7% (76 / 600) of subjects had grade 3+ anemia, 6.5% (39 / 600) of subjects had grade 3+ thrombocytopenia, and 2.2% (13 / 600) of subjects had grade 3+ neutropenia.

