#### **9.3.1 Interim Analysis for Safety**

There will be no formal interim analysis of the efficacy data.

An interim analysis of the safety data will be conducted during the study. The interim analysis will be conducted when 10 subjects have completed treatment with 6 injections of radium-223 dichloride or discontinued study treatment early. The purpose of this interim analysis is to formally review safety data and to assess whether it is acceptable to continue enrollment of subjects. The review of the safety data in this interim analysis will be conducted by the HCI Data Safety Review Committee (DSMC). A proportion of subjects with grade 3 or higher hematologic adverse events significantly more than those reported for the radium-223 arm of the Phase 3 trial would be evidence of unacceptable toxicity. In particular, four or more grade 3+ anemias, three or more grade 3+ thrombocytopenias, or three or more grade 3+ neutropenias in ten subjects would be statistically significantly higher than expected (at the one-sided 0.05 significance level). An adjustment may be made to these numbers if the proportion of patients with prior chemotherapy is higher than the 59% reported in Parker et al (2013).

A final safety analysis will be conducted when all 35 evaluable subjects have completed 6 doses of treatment, plus the end of treatment visit (30 days post-last dose), or discontinued treatment early.

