### Analysis sets

The *safety population*, which includes all subjects who receive at least one dose of study drug, will be used for the safety analysis.

The *randomized population*, which includes randomized subjects with follow up to EOT or disease progression (which ever comes earlier) will be used for the primary efficacy analysis. This population *excludes* patients enrolled prior to randomization.

The *combined population* includes all subjects treated with enzalutamide + radium-223 or enzalutamide alone with follow up to EOT or disease progression (which ever comes earlier). This population includes subjects enrolled prior to randomization with sufficient follow up. The combined population will be used for secondary and exploratory analyses.

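### The final hematologic safety test sets a proportion of patients with any of three events against a sum of three rates, and its printed null (21%) and printed count (13 of 35) disagree at 12 of 35

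*Combined protocol and SAP*

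**What the plan says.** Section 10.1.3 (Primary Safety Analyses) specifies an exact binomial test at the one-sided 0.05 level, "comparing the proportion of subjects with one or more of grade 3+ anemia, thrombocytopenia, or neutropenia to 21" percent. It then turns the test into a count: "With a safety population of 35 evaluable patients, 13 or more patients with one or more of grade 3+ anemia" or either of the other two cytopenias would indicate an unacceptable rate. The Study Summary repeats both statements and says where the 21% comes from: "In that study the sum of the proportion of subjects with grade 3+ anemia, thrombocytopenia, or neutropenia is 21" percent.

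The components are in section 3.1.4 under Bone Marrow Suppression: "12.7% (76 / 600) of subjects had grade 3+ anemia, 6.5% (39 / 600) of subjects had grade 3+ thrombocytopenia". The third component, neutropenia of the same severity, is reported there as 13 of 600, or 2.2%.

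Three further statements bear on the point:
- Section 10.1.3 also says "Exact 90% confidence intervals will be calculated for adverse events and serious AEs".
- Section 9.3.1 places the analysis at the end of treatment: "A final safety analysis will be conducted when all 35 evaluable subjects have completed 6 doses of treatment" or have stopped early.
- The Analysis sets paragraph in section 10 defines the safety population as one "which includes all subjects who receive at least one dose of study drug", which need not number 35.

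**The concern.** The statistic and its benchmark measure different things. The trial will count patients who had at least one of three events, each patient once. The benchmark adds three separate rates, so a reference patient with both anemia and thrombocytopenia enters it twice. For these three terms the sum can equal the "at least one" rate or exceed it, but cannot fall below it. Any error makes the test slower to flag excess toxicity.

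The second problem is internal to the paragraph. It gives a test (exact, one-sided 0.05, against 21%) and a count (13 of 35) as if they were the same rule. If they are not, two analysts who each follow the plan can report opposite conclusions from the same data.

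Safety and feasibility of the combination is a primary objective (section 1.1.2), and this is the formal end-of-study criterion for hematologic toxicity. The reported conclusion is what is at stake. The criterion is not a stopping rule.

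**Working it through.** **Inputs.** n = 35, one-sided 0.05, exact binomial, null 21%, count 13 (section 10.1.3). Reference events: 76, 39 and 13 of 600 (section 3.1.4). The boundary is the smallest r with P(X ≥ r) ≤ 0.05 for X ~ Binomial(35, p0).

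**Reproducing the printed count.** The sum is 76 + 39 + 13 = 128, and 128/600 = 0.2133.

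| Null p0 | P(X ≥ 12) | P(X ≥ 13) | Boundary |
|---|---|---|---|
| 128/600 = 0.2133 (unrounded sum) | 0.0535 | 0.0238 | 13 |
| 0.214 (12.7 + 6.5 + 2.2, printed percentages) | 0.0546 | 0.0243 | 13 |
| 0.21 (as printed in the test) | 0.0481 | 0.0210 | 12 |

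So 13 is correct for the unrounded sum and is not itself a miscalculation. It is not the boundary for the 21% that the test sentence prints. P(X ≥ 12) equals 0.05 at p0 = 0.2112, and rounding 21.33% down to 21% crosses that value.

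**Where test and count disagree.** Against 21%:
- 11 of 35 gives P = 0.0992, and neither rule flags.
- 13 of 35 gives P = 0.0210, and both flag.
- 12 of 35 gives P = 0.0481: the test rejects and the count does not flag.

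The exact 90% interval at 12/35 is 21.1% to 49.6%, which excludes 21% but includes 21.33%. This inverts the same one-sided test, so it shows how the conflict would appear in a report rather than adding evidence.

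P(X = 12) is 0.027 at a true rate of 21%, 0.030 at 128/600 and 0.140 at 35%. For n from 30 to 41, the two nulls give different boundaries only at n = 35 (both give 12 at n = 34 and 13 at n = 36 to 38).

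**Sum against "at least one".** With d duplicates among the 128 events (entries for patients already counted), the comparable null is (128 − d)/600. The limits are d = 0 (no overlap, 21.33%) and d = 52 (every event nested within anemia, 76/600 = 12.67%).

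| Duplicates d | Null at start of range | Boundary | P at boundary | P one below |
|---|---|---|---|---|
| 0–1 | 128/600 = 0.2133 | 13 | 0.0238 | 0.0535 |
| 2–15 | 126/600 = 0.2100 | 12 | 0.0481 | 0.0992 |
| 16–29 | 112/600 = 0.1867 | 11 | 0.0489 | 0.1028 |
| 30–43 | 98/600 = 0.1633 | 10 | 0.0489 | 0.1055 |
| 44–52 | 84/600 = 0.1400 | 9 | 0.0477 | 0.1069 |

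As one reference point, assume independence: 1 − (1 − 76/600)(1 − 39/600)(1 − 13/600) = 0.2011. Then P(X ≥ 11) = 0.0772, P(X ≥ 12) = 0.0357 and P(X ≥ 13) = 0.0148. The boundary is 12, and a count of 13 tests at 0.015 rather than near 0.05.

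**Cost of one patient.** If the proper boundary is 12, the chance of flagging with 12 against 13 is 0.348 against 0.227 at a true rate of 30%, and 0.598 against 0.458 at 35%.

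**The case against.** The strongest reply has four parts.

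1. **The count of 13 is right for the components in section 3.1.4, and the conflict has a narrow trigger.** It needs exactly 12 events and, over a plausible range of n, exactly 35 patients. The safety population is defined by at least one dose and up to 50 patients may be enrolled, so the number of radium-treated patients analysed may not be 35. All of this stands. It makes the rounding part cheap to fix and unlikely to bite, but 35 is the number the plan itself uses.
2. **The sum is disclosed as a sum, and the size of the overlap error is unknown.** This is also correct. The documents fix the direction for the three named terms, not the amount. There is one way out of even the direction: Table 3 lists grade 3–4 pancytopenia at 1%. Suppose those patients (3 to 8 of 600, allowing for rounding) were coded apart from the three terms and counted toward the composite. The null would then be 131/600 to 136/600, or 21.8% to 22.7%, and 13 would remain the boundary (P(X ≥ 12) = 0.062 to 0.079). Disclosure does not turn a sum into the proportion being tested.
3. **The consequences are limited.** The interim limits in section 9.3.1 compare each cytopenia with its own rate and are free of the problem. Section 7.1.1 has patient-level rules, and section 13.3 provides quarterly committee review. This stands and caps the severity.
4. **Section 10.1 names grade 3+ non-hematological events as the primary safety endpoint.** Even so, section 10.1.3, headed as the primary safety analysis, gives a formal test and count only for hematologic events.

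**Conclusion.** Both parts hold.

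The contradiction between test and count is certain and needs no assumption. At 12 of 35 the printed test calls the rate unacceptable and the printed count does not.

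The mismatch of definitions is also certain: a proportion of patients with at least one event is compared with a sum of three rates. For the three terms as named, the benchmark can err only toward leniency. How far is unknown. Depending on the overlap, the count is too high by zero to four patients (boundary 13 down to 9). Thirteen survives only if at most one of the 128 events is a duplicate, or if separately coded pancytopenia cases raise the comparable rate. Independence, which is an assumption, gives 12.

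This should be fixed before the final safety analysis. It affects the reported safety conclusion, not the conduct of the trial.

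**What to change.** - Use as the null the reference trial's proportion of patients with at least one of the three events. If it cannot be obtained, state that 21.3% is an upper bound for the three named terms and show the boundary across 12.7% to 21.3%.
- Print the null as a fraction or unrounded (128/600 if the sum is kept), so that test and count agree.
- Derive the count from that null for the number of radium-treated patients actually analysed, instead of fixing it at 35.
- Make the same correction in section 10.1.3 and the Study Summary.

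The cost is a few lines of wording and one data request; the rounding conflict alone needs only the unrounded null. The trade-off is a higher chance of a false flag if the boundary falls. A boundary of 12 has level 0.036 if the comparable rate is 20.1%, and 0.0535, slightly over the nominal 0.05, if there was in fact no overlap.

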## STUDY SUMMARY

Title	A Phase 2 Randomized Study comparing Radium Ra 223 dichloride + Enzalutamide with Enzalutamide alone in Men with Metastatic Castration Refractory Prostate Cancer
Short Title	Radium Ra 223 dichloride + Enzalutamide with Enzalutamide alone in mCRPC
Protocol Number	IRB # 68770
IND	IND Exempt (121340)
Phase	Phase 2
Design	Open label, randomized two arm study in men with progressive metastatic CRPC who are candidates for treatment with enzalutamide alone or enzalutamide + Radium Ra 223 dichloride
Study Duration	3.5 years
Study Center(s)	Single-center - Huntsman Cancer Institute
Objectives	
Primary:
 
 
1. To measure the difference between the levels of markers of bone formation (Procollagen Type 1 intact N-terminal Propeptide [NTP] and bone alkaline phosphatase [BAP]) and resorption (N-telopeptide [NT], C-Telopeptide beta-cross linked [CTB], pyridinoline) in serum collected at baseline (C1D1), C3D1, C5D1, EOT and at disease progression (whichever comes earlier) in two arms.
 
2. To establish safety and feasibility of combining enzalutamide and radium-223.
 
 
Secondary:
 
The secondary objectives will compare the two arms for the following:
 
 
1. Time to progression in serum PSA, total ALP concentrations, and radiological progression.
 
2. Response rates by serum PSA, total ALP concentrations.
 
3. Time to first skeletal related event.
 
4. Percent change in opioid use (morphine equivalent) during protocol treatment.
 
5. Overall Survival at 2 years post enrollment.
 

Number of Subjects	47 patients (50 total to account for any inevaluable patients). Combination Arm – 35 evaluable patients (27 randomized patients + 8 patients enrolled prior to randomization who will be used for secondary and exploratory analyses only). Control Arm (enzalutamide alone) – 12 evaluable patients.

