**Figure 1: Initial Single Arm Non-Randomized Design Changed to Two Arm Randomized 2 to 1 Design**

Only those patients enrolled on the randomized portion of the trial will be used for primary endpoint analysis. Patients enrolled on the non-randomized portion will be used for secondary and exploratory analyses only.

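### The primary hematologic safety limit counts 8 patients whom other sections confine to secondary and exploratory analyses, so the plan leaves two decision rules: 10 of 27, or 12 to 13 of 35

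*Combined protocol and SAP*

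**What the plan says.** Section 10.1 lists efficacy, safety and feasibility as co-primary. It applies the safety population to every safety analysis, by treatment arm. Section 10.1.3, headed as the primary safety analysis, then specifies the test: "An exact binomial test will be performed at the one sided 0.05 significance level comparing the proportion of subjects" with at least one of three grade 3+ cytopenias to a reference rate. That rate is the sum of the proportions in the phase 3 radium-223 arm "with grade 3+ anemia, thrombocytopenia, or neutropenia is 21" percent. The limit follows: "With a safety population of 35 evaluable patients, 13 or more patients with one or more of grade 3+ anemia", thrombocytopenia or neutropenia. The Study Summary repeats it.

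Three other statements bear on who is counted:

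- Section 4.1, text under Figure 1: "Only those patients enrolled on the randomized portion of the trial will be used for primary endpoint analysis". The Study Summary and Section 4.2 describe the combination arm as 27 randomized patients plus "8 patients enrolled prior to randomization who will be used for secondary and exploratory analyses only".
- Section 10, Analysis sets, defines the safety population as the set "which includes all subjects who receive at least one dose of study drug, will be used for the safety analysis". Section 9.3 agrees. Neither adds an evaluability condition, and neither excludes the patients enrolled before randomization.
- Section 9.3.1: "A final safety analysis will be conducted when all 35 evaluable subjects have completed 6 doses of treatment". The sentence goes on to cover the end-of-treatment visit and patients who stopped early.

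**The concern.** A number of 35 in the combination arm exists only if the 8 non-randomized patients are counted. Taken at face value, Sections 4.1 and 4.2 exclude them from any primary analysis, and safety is co-primary. The literal denominator would then be 27. Section 10.1.3 also joins two different ideas by describing a safety population of evaluable patients, although the safety population depends only on having been dosed.

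At stake is the rule that declares hematologic toxicity unacceptable. If the denominator is settled after events are known, the verdict can depend on which section the analyst chose to follow.

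**Working it through.** **Inputs**

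- Test: exact binomial, one-sided 0.05 (Section 10.1.3).
- Null rate p0: printed as 21% (Section 10.1.3). Section 3.1.4, under Bone Marrow Suppression, gives the components: "12.7% (76 / 600) of subjects had grade 3+ anemia, 6.5% (39 / 600) of subjects had grade 3+ thrombocytopenia", and 13/600 with neutropenia. The sum is (76 + 39 + 13)/600 = 128/600 = 21.33%. I take the plan's rate as given.
- Denominators: 27 (randomized combination arm), 35 (27 + 8), and 36 to 38. Section 4.2 allows 50 enrolled for 47 evaluable, so 3 are spare. That all 3 might fall in the combination arm is my assumption.

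**Formula.** The limit is the smallest r for which P(X ≥ r | n, p0) ≤ 0.05, with X binomial.

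**The plan's own figure, n = 35**

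- p0 = 128/600: P(X ≥ 12) = 0.0535 and P(X ≥ 13) = 0.0238. The limit is 13, as printed.
- p0 = 21%: P(X ≥ 12) = 0.0481 and P(X ≥ 13) = 0.0210. The limit is 12.

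So 13 reproduces from the unrounded rate, and not from the 21% that the test is said to use.

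**Limit by denominator**

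| n | Who is counted | Limit (P) at 21% | Limit (P) at 128/600 |
|---|---|---|---|
| 27 | randomized only | 10 (0.0414) | 10 (0.0456) |
| 35 | randomized plus the 8 | 12 (0.0481) | 13 (0.0238) |
| 36 | all treated, 1 spare | 13 (0.0267) | 13 (0.0301) |
| 37 | all treated, 2 spare | 13 (0.0334) | 13 (0.0376) |
| 38 | all treated, 3 spare | 13 (0.0413) | 13 (0.0463) |

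**Can the choice reverse a verdict?** Yes, in either direction. These counts are invented for illustration, against 21%.

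- 10 of 27 randomized and 1 of the 8: 10/27 gives P = 0.0414 (unacceptable); 11/35 gives P = 0.0992 (acceptable).
- 9 of 27 randomized and 4 of the 8: 9/27 gives P = 0.0948 (acceptable); 13/35 gives P = 0.0210 (unacceptable).

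With exactly 12 of 35, the rounding of p0 alone decides.

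**Power.** The plan states no alternative rate. If the true rate were 40% (my assumption), power would be 0.69 for 10 of 27, 0.81 for 12 of 35 and 0.69 for 13 of 35. At an assumed 35% the figures are 0.48, 0.60 and 0.46.

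**The case against.** The strongest reply is that the plan already names the denominator. Section 10.1 applies the safety population to all safety analyses by arm, and Sections 9.3 and 10 define it as everyone dosed. The pre-randomization patients are excluded only from the randomized population, which serves the primary efficacy analysis. Section 10 and Section 10.1.1 use the singular primary endpoint for the N-telopeptide change, so the Section 4.1 sentence may mean only that. And since 35 requires the 8, Section 10.1.3 evidently meant to count them. This stands as the better reading. It does not remove the sentences in the Study Summary and Section 4.2, which confine the 8 without reference to any endpoint.

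A reader might go further and infer that the word evaluable drops patients who stopped early for cytopenia and so tilts the test toward an acceptable result. The documents do not support that. Section 9.3.1 expressly includes patients who discontinued early. Section 6.6 lets some withdrawn or inevaluable patients be replaced, but nothing there removes a dosed patient from the safety population. Nor does moving from 35 to all treated shift the printed limit: it is 13 at 36 to 38 under either p0.

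A reader might also pair the limit of 13 with 27 patients, which gives a size of only 0.0015 to 0.0018. Because the test is exact, P would be computed at the number actually analyzed, so that combination is not something the plan prescribes.

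**Conclusion.** The inconsistency is real and affects a decision rule. Without the 8 the limit is 10 of 27. With them it is 12 of 35 at 21% or 13 of 35 at 128/600. The all-treated combination-arm reading has the better textual support, but the plan should not leave it to inference. The documents do not show that the plan as written is biased toward declaring the toxicity acceptable.

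The limits for 27 and 35 rest only on figures in the plan. The range 36 to 38 assumes that the spare places go to the combination arm, and the power figures assume true rates that the plan does not give.

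A related contradiction needs settling at the same time: Section 10.1 names grade 3 or higher non-hematological events as the primary safety endpoint, whereas Section 10.1.3 tests hematologic ones.

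**What to change.** 1. In Section 10.1.3 and the Study Summary, define the test set as all combination-arm patients who received at least one dose, including the 8 enrolled before randomization and any patient later replaced. Remove the word evaluable there, and align Section 9.3.1.
2. In Sections 4.1 and 4.2 and the Study Summary, limit the secondary-and-exploratory restriction on the 8 to the randomized N-telopeptide comparison.
3. State p0 either as 128/600, or as 21% with a limit of 12 at n = 35. Replace the fixed 13 of 35 with the exact test at the realized n, noting that the limit is 13 for 36 to 38 treated under either p0. Keeping 13 alongside an exact test against 21% would give opposite verdicts at 12 of 35.
4. Reconcile the primary safety endpoint named in Section 10.1 with the test in Section 10.1.3.

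The cost is a wording amendment in a few places, with no new data and no change in enrollment. It should be made before the final safety result is examined by arm.
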